3.3.4 COVID-19 Periods

Two COVID-19 periods are considered for analysis:

- During Pandemic: All study participants enrolled until the day before the date when the WHO declared that COVID-19 no longer constitutes a public health emergency of international concern.
- Post Pandemic: All study participants enrolled on or after the date when the WHO declared that COVID-19 no longer constitutes a public health emergency of international concern.

A pre-pandemic period is not considered as the first study participant was enrolled after 11 Mar 2020, the date the WHO declared the outbreak of COVID-19 pandemic. The WHO declared that COVID-19 no longer constitutes a public health emergency of international concern on 5 May 2023.

3.3.5 Completion/Early Discontinuation/Ongoing

Each study participant will be considered as completing the study or discontinuing the study early. While the study is ongoing they may also be considered as ongoing.

A study participant will meet the criteria for completion if they meet one of the following criteria:

- They attend the FV and transition to another BRV study or a managed access program or convert to commercial BRV (as indicated on the FV eCRF by answering “Yes” to the question “Will the study participant be prescribed Brivaracetam after the EP0132 study (eg participant is transitioning to another BRV study, managed access program or converting to commercial BRV)?”)

- The investigator determines they have completed the study following the participant attending the FV
- For participants where a dose of $>1\text{mg/kg/day}$ ($>50\text{mg/day}$ for study participants with body weight $\geq 50\text{kg}$) is reached at FV: they attend the FV and subsequently down-titrate, attending the DTV and SV. If the participant does not attend both the DTV and SV after down-titration, they are not considered a completer.
- For participants where a dose of 1mg/kg/day (50mg/day for study participants with body weight $>50\text{kg}$) is reached at FV: they attend the FV and attend the SV, as down-titration is not required for these participants.

A study participant will be regarded as discontinuing the study early if they do not meet the criteria for completion.

3.3.6 Data sources for EP0132 EV

The EV in EP0132 is also the last completed study visit of N01269. Information at this visit will be obtained from either the N01269 analysis database or the EP0132 eCRF dependent on the data type. The last completed visit in N01269 will be one of the following:

- Visit 6
- Visit 7
- EDV

The following will be obtained from the N01269 analysis database, if available:

- Absence seizure diagnosis (CAE/JAE)
- Race
- Ethnicity
- Gender
- Neurological examination
- Psychiatric and mental status
- Vital signs
- Body weight and height
 - Height is measured only at Visit 6 in N01269 and is not scheduled at Visit 7 or EDV. Height at the EP0132 EV will therefore be obtained from the Visit 6 assessment if available and will be otherwise missing.
- Laboratory assessments
 - EpiTrack Junior
 - PedsQL
 - ECG

The following will be obtained from the EP0132 EV eCRF:

- Age in years and months
- AEs*
- Previous and concomitant medications*

*Adverse events and concomitant medications will be summarized as reported on the EP0132 eCRF without integration from the N01269 analysis database. Any AEs or medications that are ongoing at the time of entry into EP0132 will be entered on the EP0132 eCRF.

In the event that the date of EV in EP0132 is later than the date of the last visit in N01269 additional unscheduled assessments may be performed for those measurements indicated above. In this case the unscheduled assessments performed after the last visit in N01269 and before or on the date of the EV in EP0132, will be used in any listings and summaries instead of those performed at the last visit in N01269.

EpiTrack Junior and PedsQL values obtained from the N01269 database for the EP0132 EV will be listed only.

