1.3 Schedule of activities**Table 1–2: Schedule of activities**

| Study period | Evaluation Period | | | | | | Down-Titration Period | Safety Period |
|--|-------------------|------------------------|--|---|--|----------------------|-----------------------|---------------|
| | EV ^a | TC | MEV | FEV | YEV/EDV ^b /EV | UV | | |
| Frequency | | After 2 weeks ± 2 days | Months 3 and 9 during each year of participation | Month 6 during each year of participation | Month 12 during each year of participation (YEV)/ Month 24 or later (FV) | | | |
| Procedures | | | | | | | | |
| Written informed consent | X | | | | | | | |
| Assent form (if applicable) | X | | | | | | | |
| Study participant identification card | X | | | | | | | |
| Inclusion/exclusion criteria | X | | | | | | | |
| Prior and concomitant medications and medical procedures | X | | X | X | X | X | X | X |
| IXRS | X | | X | X | X | X | X | X |
| Recording of AEs | X | X | X | X | X | X | X | X |
| Study drug dispensed | X | X (as applicable) | X | X | X ^d | X (as applicable) | | |
| Study drug returned ^e | | | X | X | X | X (as applicable) | X | |
| Participant diary dispensed | X | | X | X | X ^d | | X | |

| Study period | Evaluation Period | | | | | | Down-Titration Period | Safety Period |
|---|-------------------|----------------------------|--|---|--|----------------|-----------------------|----------------|
| | EV ^a | TC | MEV | FEV | YEV/EDV ^b /FV | UV | | |
| Frequency | | After 2 weeks \pm 2 days | Months 3 and 9 during each year of participation | Month 6 during each year of participation | Month 12 during each year of participation (YEV)/ Month 24 or later (FV) | | | |
| Procedures | | | | | | | | |
| Participant diary retrieved | | | X | X | X | | X | |
| Assessment of childbearing potential | | | X | X | X | | | |
| Complete physical/neurological examination ^f | | | | X | X | | | X |
| Brief physical/neurological examination ^g | | | X | | | X | | |
| Psychiatric and mental status | | | | X | X | | | X |
| Vital signs ^h | | | X | X | X | | X | X |
| Dose adaptation (optional) | | X | X | X | X | X | | |
| Body weight, height | | | X | X | X | | | |
| Laboratory assessments for safety ⁱ | | | X | X | X | | | X ^j |
| BRV plasma concentration ^k | | | | X | X | | | |
| C-SSRS ^l | | | X | X | X | X ^m | X | X |
| EpiTrack Junior ⁿ | | | | X | X | | | X |
| PedsQL ⁿ | | | | X | X | | | |
| ECG ^o | | | | | X | | | X ^j |

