| Study period | Evaluation Period | | | | | | Down-Titration Period | Safety Period |
|------------------------------|-------------------|------------------------|--|---|--|-------------------|-----------------------|---------------|
| | EV ^a | TC | MEV | FEV | YEV/EDV ^b /FV | UV | | |
| Frequency | | After 2 weeks ± 2 days | Months 3 and 9 during each year of participation | Month 6 during each year of participation | Month 12 during each year of participation (YEV)/ Month 24 or later (FV) | | | |
| Procedures | | | | | | | | |
| EEG (1h EEG/HV) ^p | | | | X | X | X (as applicable) | | |
| End of study status | | | | X ^q | | | | X |

AE=adverse event; AED=antiepileptic drug; ALP=alkaline phosphatase; ALT=alanine aminotransferase; AST=aspartate aminotransferase; BRV=brivaracetam; C-SSRS=Columbia-Suicide Severity Rating Scale; DTV=Down-Titration Visit; ECG=electrocardiogram; eCRF=electronic case report form; EDV=Early Discontinuation Visit; EEG=electroencephalogram; EV=Entry Visit; FEV=Full Evaluation Visit; FV=Final Visit; GGT=gamma-glutamyltransferase; HV=hyperventilation; IXRS=interactive voice or web response system; MEV=Minimal Evaluation Visit; PedsQL=Pediatric Quality of Life Inventory; PK=pharmacokinetic; S=on-site visit; SAE=serious adverse event; SV=Safety Visit; TC=telephone call; UV=Unscheduled Visit; YEV=Yearly Evaluation Visit

^a The EV is also the last completed study visit of N01269. The following Baseline data will be obtained from N01269 and should not be recorded on the eCRF for this study's EV: demographics, general medical and procedure history, epilepsy history, AED history, seizure count/ absence seizure count, ECG, laboratory assessments for safety, vital signs, body weight, height, physical and neurological examinations, psychiatric and mental status, and recording of epileptic seizures.

^b Participants who discontinue from the study before Month 24 will complete an EDV, unless the participant is transitioning to another BRV study, in which case an FV will be completed (see Section 4.1).

^c Visit should be scheduled at the end of the Down Titration Period. The duration of the Down Titration Period will depend on when the final dose of the study drug was taken during the Evaluation Period, with a maximum duration of 4 weeks. Study participants requiring down titration will complete their daily seizure diaries during the Down-titration Period.

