6.3 Medical history, procedure history, and concomitant medical procedures

Medical history, procedure history, and concomitant medical procedures will be reported as collected on the EP0132 eCRF only – no integration of data from the N01269 analysis database will be performed. Ongoing conditions that initially occurred after the time of entry into N01269 will be recorded as an AE, not as medical history on the EP0132 eCRF. Only conditions that occurred prior to N01269, that were not captured in N01269 database, should be entered as medical history on the EP0132 eCRF.

Listings of medical history conditions and glossary for the SS will be provided.

Procedure history and concomitant medical procedures will not be summarized. Listings of procedure history and concomitant medical procedures will be provided, based on the SS.

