6.4 Previous and concomitant medications

Medications will be summarized as reported on the EP0132 eCRF without integration of medications from the N01269 analysis database. Any medications that are ongoing at the time of entry into EP0132 will be entered on the EP0132 Concomitant Medications eCRF.

Medications will be classified into the following categories:

- Previous medication: includes any medications that ended prior to the first dose of study drug in EP0132
- Concomitant medication: includes any medications with at least one day in common with study treatment in EP0132 (including down-titration)
 - Includes medications that started prior to the first dose of study drug in EP0132 and continued after
 - Includes medications that started during treatment in EP0132
- Follow-up medication: includes any medications that started after the final dose of study drug in EP0132. Final dose of study drug includes down-titration medication, therefore follow-up medications are those with a start date during the Safety Period.

The number and percentage of study participants taking previous and concomitant non-AED medications will be summarized overall, and by anatomical main group (Anatomical Therapeutic Chemical [ATC] classification level 1), therapeutic subgroup (ATC classification level 2), and preferred drug name for the SS. Study participants reporting multiple medications within an ATC class are counted once per medication and class.

The number and percentage of study participants who took previous and concomitant AEDs, including benzodiazepines, will be summarized by preferred drug name for the SS.

The identification and classification of medications as AED, including benzodiazepines, will be performed by merging an external physician-reviewed spreadsheet (which includes relevant flags for selecting AED medications or benzodiazepines) with the data entered into the study database in order to categorize the medications correctly for the tables.

For summarization, similar AEDs are grouped and summarized together under the following groups:

- Valproate
- Phenobarbital
- Phenytoin

The medications to be included in each of the above groups are also flagged in the spreadsheet referred to above. Combination AEDs are not considered for grouping.

All medications will be listed for the SS.

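### Previous AEDs are summarised from the EP0132 eCRF alone, although the protocol leaves AED history in N01269, so AEDs stopped before entry may be materially under-reported

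*SAP*

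**What the plan says.** **Protocol, Table 1–2 (Section 1.3).** Footnote a, attached to the Entry Visit (EV), reads in part: "The following Baseline data will be obtained from N01269 and should not be recorded on the eCRF". The items it names include "epilepsy history, AED history, seizure count/ absence seizure count". The same table also has a row titled "Prior and concomitant medications and medical procedures", which is ticked at the EV.

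**SAP 3.3.6.** Two lists set out where EV data come from. The N01269 list covers syndrome, demographics, examinations, vital signs, laboratory data, ECG, EpiTrack Junior and PedsQL. It does not contain AED history or the absence seizure count. The EP0132 eCRF list contains "Previous and concomitant medications", with a note: "Adverse events and concomitant medications will be summarized as reported on the EP0132 eCRF without integration from the N01269 analysis database".

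**SAP 6.4.** The bar on integrating N01269 data is repeated for medications in general, so it reaches previous as well as concomitant drugs. A previous medication is one that ended before the first EP0132 dose, and no look-back limit is set. The planned output is a count and percentage for the Safety Set: "participants who took previous and concomitant AEDs, including benzodiazepines, will be summarized by preferred drug name".

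**SAP 6.3, for comparison.** Medical history has a similar split between the two studies: "Only conditions that occurred prior to N01269, that were not captured in N01269 database, should be entered as medical history". Here the SAP provides listings only and no percentages.

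**The concern.** The protocol puts AED history in one database and the SAP reads previous AEDs from the other. A site that follows footnote a leaves an AED stopped before entry off the EP0132 eCRF. The SAP then does not retrieve it from N01269, but still counts over a definition that includes it.

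What is at stake is how the cohort is described. Efficacy in this single-arm study is reported as uncontrolled seizure-freedom percentages, and prior AED exposure is part of the context a reader needs to interpret them. Protocol 2.1 itself stresses drug resistance in CAE, although its figure of about one third comes from a cited study and not from this cohort. Protocol 2.1 also describes N01269 as a monotherapy study. AEDs stopped before or during it are therefore plausibly a real part of these participants' history; that last step is inference, since the documents give no counts.

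**Working it through.** The plan gives no figure for previous AEDs, so there is nothing to reproduce. The check compares the texts and then applies the SAP's own date definitions.

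**1. Sources side by side**

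| Item | Protocol Table 1–2, footnote a | SAP 3.3.6 and 6.4 |
|---|---|---|
| AED history | From N01269; should not go on the EP0132 EV eCRF | Not on the N01269 list |
| Previous AEDs | Row for prior medications ticked at the EV | EP0132 eCRF only, no integration; percentages planned |
| AEDs ongoing at entry | Not addressed in footnote a | Entered on the EP0132 eCRF; concomitant AED table |
| Absence seizure count | From N01269; should not go on the EP0132 EV eCRF | Not on the N01269 list, nor in the Baseline list of SAP 3.5 |

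SAP 3.12, which sets out changes from the protocol, covers concomitant AED use, truncation at Month 24 and the EpiTrack Junior age correction. It does not mention this source question.

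**2. Date logic**

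Let V be the EV date, D the date of the first EP0132 dose, and E the date an AED ended.

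- Previous (SAP 6.4): E < D.
- Concomitant (SAP 6.4): at least one day shared with EP0132 treatment. For a drug already in use at entry this means E ≥ D.
- Expected timing (SAP 3.3.2): first dose on the evening of the EV, so D = V.

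*Reading A: sites enter only medications ongoing at entry, so E ≥ V.* With D = V, every entry has E ≥ D and is concomitant, so the previous set is empty. If D = V + k days, only drugs with V ≤ E < V + k are previous, that is, those stopped in the k days between the visit and the first dose.

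*Reading B: sites also record prior medications at the EV, as the Table 1–2 row suggests.* The previous set then holds whatever sites choose to enter. It still lacks any AED history held only in N01269.

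The documents do not settle A against B. The result runs from an empty previous-AED table to an incomplete one of unknown size.

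**3. Scale**

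Percentage shown = (participants with a previous AED − participants whose previous AEDs are all missing from the eCRF) / N. Neither count is in the documents. Assuming that N is close to the planned 140, each participant missed lowers the overall percentage by 1/140 = 0.7 percentage points.

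**The case against.** The best case for the plan has five parts.

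- **Sites may well record prior AEDs.** Table 1–2 ticks prior medications at the EV, and SAP 3.3.6 names previous medications as an EP0132 item. SAP 4.1.4.3 has date rules for medications not ongoing from N01269. SAP 6.4 says that ongoing drugs will be entered but does not limit entry to them, whereas the medical history text in 6.3 does set such a limit. This stands. A reader might infer that the table is bound to be nearly empty, but that needs Reading A, which the documents do not state. Nor does Reading B rescue the percentage: a general row sits beside a specific footnote on AED history, and sites may follow either.
- **Ongoing AEDs are shown.** This stands. A reader might infer that participants would appear untreated, but AEDs continuing at entry go into the concomitant AED table. That table cannot show AEDs already stopped.
- **The scope is declared.** SAP 3.2 says outputs use EP0132 data unless otherwise specified. This helps a reader of the SAP. It does not help someone who reads a table of previous AEDs whose definition has no look-back limit.
- **No protocol-defined analysis is dropped.** Protocol 9.2 to 9.4 plan no summary of AED history or Baseline seizure count, and footnote a governs only where data are recorded. This stands, and it softens the silence of SAP 3.12. The source mismatch is still unexplained anywhere in the SAP.
- **The missing seizure count is a separate matter.** This stands. It has no effect on the AED table. All planned efficacy endpoints are seizure-freedom proportions, and none is a change from a Baseline count. SAP 6.2 already brings forward the diagnosis date for epilepsy duration, age at diagnosis and percent of life with epilepsy.

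**Conclusion.** The point holds as a mismatch of sources. The SAP plans percentages of the Safety Set with previous AEDs from a source that, under footnote a, should not contain AED history, and it bars the database that does. AEDs stopped before EP0132 entry may be materially under-reported.

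The size cannot be estimated. It depends on how many participants had stopped an AED and on how sites reconciled footnote a with the medication row, and the documents give neither. The conclusion assumes only that at least some sites follow footnote a; the protocol's wording there is advice (should not) and not an absolute bar.

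The reach is limited to one descriptive table. No primary safety result, secondary efficacy result, denominator or responder classification depends on it.

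**What to change.** **Preferred.** In SAP 3.3.6, add AED history to the items obtained from the N01269 analysis database. In SAP 6.4, derive previous AEDs from that history plus EP0132 entries that ended before the first EP0132 dose, counting each drug once per participant. When specifying the merge, confirm that AEDs stopped during N01269 are included, since the documents do not say where N01269 stores them. Add a line on the source to SAP 3.12.

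**If integration is not feasible.** Drop the previous-AED percentages and list the entries, labelled as EP0132-reported only, with a cross-reference to N01269. SAP 6.3 already takes the listing-only route for medical history.

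**Separate and optional.** Because footnote a also assigns the absence seizure count to N01269, summarise it in SAP 6.2 as descriptive context.

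**Cost.** SAP wording and a merge with a database the SAP already uses for other Baseline variables; no new data collection. Whether the N01269 AED history is held in a form that merges easily cannot be checked from these documents, which is why the listing-only fallback is given.

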3.3.7 Mapping of assessments performed at EDV

Efficacy and safety assessments at an EDV will be summarized at the corresponding scheduled visit if the assessment was planned at that visit. An assessment is considered to correspond to a scheduled visit if it falls within the protocol-specified visit window. Assessments performed at an EDV that is not within the protocol-specified visit window of a scheduled visit will not be mapped to a scheduled visit. Re-mapped data will be displayed in the by visit summary tables only if the assessment was planned for that particular visit.

If any particular assessment data are already recorded at the given scheduled visit, data from the EDV visit will not be re-mapped. For example, if an EDV is performed within the same protocol-specified visit window as an existing scheduled MEV/FEV/YEV (eg Month 12) and a participant has a particular assessment (eg neurological examination) present at both Month 12 and EDV, then the neurological examination data from the EDV will not be re-mapped to Month 12.

Data will be re-mapped on a ‘per assessment’ basis where assessments are grouped as follows:

- All assessments from the neurological examination
- All assessments from the psychiatric and mental status assessments
- All vital signs assessments (systolic blood pressure, diastolic blood pressure, respiratory rate, pulse rate and temperature)
- All hematology assessments
- All clinical chemistry assessments
- All endocrinology assessments
- All urinalysis assessments
- All ECG assessments
- All EEG assessments

- Height and body weight
- All C-SSRS assessments
- All EpiTrack Junior assessments
- All PedsQL assessments

The groupings above define the measurements that will be retained together for any re-mapping. If at least one data point from a group of assessments is already available at the respective scheduled visit (eg, systolic blood pressure), the data at the EDV will not be re-mapped.

Handling of EEG assessments occurring at EDVs that are not mapped to scheduled visits is described in [Section 3.13.8](#).

3.3.8 Mapping of assessment performed at FV

Efficacy and safety assessments at a FV will be summarized at the corresponding scheduled visit if the assessment was planned at that visit. An assessment is considered to correspond to a scheduled visit if it falls within the protocol-specified visit window. FVs will be mapped to scheduled visits using the approach outlined in [Section 3.3.7](#).

Handling of EEG assessments occurring at FVs that are not mapped to scheduled visits is described in [Section 3.13.8](#).

3.3.9 Mapping of assessments performed at UV

Assessments performed at unscheduled visits will not be remapped to any scheduled visit or EDV or FV, except in the following scenarios:

- Unscheduled assessments performed after the last visit in N01269 and on or before the date of the EV in EP0132 ([Section 3.3.6](#))
- Unscheduled assessments performed for participants that remain in EP0132 study beyond 2 years (Month 24) before they complete or withdraw from the study. These unscheduled assessments will be mapped to scheduled visits using the approach outlined in [Section 3.3.7](#). In the situation where there are two unscheduled visits mapped to the same scheduled visit, the visit nearest to the scheduled day as defined in [Table 3-5](#) will be used. If the two unscheduled visits are the same distance away from the scheduled day, the earliest visit will take priority.
 - If an assessment is missing at the mapped visit, the missing assessment may be obtained from the alternative unscheduled visit, only if the entire group of assessments are missing (Assessments will be grouped as specified in [Section 3.3.7](#)). For example, if only systolic blood pressure is present at the mapped visit, diastolic blood pressure, respiratory rate, pulse rate and temperature will not be obtained from the alternative unscheduled visit.

Handling of unscheduled EEG assessments is described in [Section 3.13.8](#).

